#### 4.1.3 Exclusion Criteria

Subjects who meet any of the following criteria will be excluded from this study:

- Pregnancy (positive pregnancy test) or lactation
- Premenopausal women not using adequate contraception. The following are considered effective means of contraception: surgical sterilization or use of oral contraceptives, barrier contraception with either a condom or diaphragm in conjunction with spermicidal gel, an IUD, or contraceptive hormone implant or patch.

- Intravitreal steroid or periocular steroid treatment within 3 months of study entry
- Focal/grid laser photocoagulation treatment within 3 months of study entry
- Panretinal photocoagulation treatment within 3 months of study entry
- Prior vitrectomy in the study eye
- History of retinal detachment in the study eye
- Prior trabeculectomy or other filtration surgery in the study eye
- Active intraocular inflammation in either eye
- Active ocular or periocular infection in either eye
- Active scleritis or epicscleritis in either eye
- History of any other retinal vascular disease (e.g., retinal vein occlusion, retinal artery occlusion)
- Coexistent retinal disease other than diabetic retinopathy (e.g., AMD, inherited retinal disease)
- Intraocular surgery within 3 months of study entry.
- History of corneal transplant or corneal dystrophy
- Significant media opacities in study eye which may interfere with visual acuity
- Participation as a subject in any clinical study within 3 months of study entry.
- History of allergy to topical iodine
- Any other condition that the investigator believes would pose a significant hazard to the subject if the investigational therapy were initiated
- Participation in another simultaneous medical investigation or trial

# 4.2 METHOD OF TREATMENT ASSIGNMENT

Randomization to the two treatment groups will be utilized. The study is not masked.

# 4.3 STUDY TREATMENT

# 4.3.1 Formulation

Ranibizumab is formulated as a sterile solution aseptically filled in a sterile,3-mL stoppered glass vial. Each single-use vial is designed to deliver 0.05 mL of 6 mg/mL ranibizumab aqueous solution with 10 mM histidine *HCI*, 10%,  $\alpha$ -trehalose dihydrate, and 0.01% polysorbate *20*, *pH 5.5*. The results in the delivery of a 0.3 mg dose of ranbizumab. Each vial contains no preservative and is suitable for **single use only**.

Further details and molecule characterization will be included in the Investigator Brochure.

# 4.3.2 Dosage, Administration, and Storage

#### a. Dosage

Subjects will be randomized to two equal size treatment groups. The first group will be treated with 0.3 mg ranbizumab monthly for the duration of the study. The second group will be treated with 0.3 mg monthly for the first three months and will subsequently be treated with 0.3 mg on a "treat-and-extend" protocol (as outlined in 4.3.2b).

#### b. Administration

Group 1 will undergo monthly intravitreal injections of 0.3 mg ranibizumab administered 30 days (+/- 7 days) following the last treatment for 12 months. Injections will be performed with sterile technique as outlined in appendix B.

Group 2 will be assigned to a "treat-and-extend" protocol. Eyes will be treated with 3 loading doses at 30-day (+/- 7 days) intervals. After the third loading dose, the follow-up interval is determined with an OCT-based protocol:

• **Criterion A:** If the central subfield thickness is less than or equal to 300 microns or there is complete absence of intraretinal or

subretinal fluid on the macular cube, the follow-up interval is increased by 2 weeks (+/- 7 days) at each visit [to a maximum interval of 12 weeks (+/- 7 days)]. The eye receives an intravitreal ranibizumab injection at every visit.

- Criterion B: If on subsequent follow-up visits, the thickness increases above 300 microns or there is recurrence of fluid with thickness above 300 microns, the interval is reduced by 2 weeks (+/-7 days) (to a minimum interval of 4 weeks). Designated visits will also occur at 6 months and 12 months for visual acuity, ocular examination, FA, and OCT. No treatment will occur at these visits unless the time coincides with the scheduled "treat-and-extend" visit.
- Criterion C: Rescue criteria If on subsequent follow-up visits, a
  patient loses > 15 letters with associated recurrence of fluid or
  central subfield thickness above 300 microns, the dosing interval will
  be immediately reduced to 4 weeks (+/- 7 days) for the next followup visit and for the residual duration of the study.
- Criterion D: Intervals following recurrence of fluid. If criterion B is met at any time, the patient will be reduced to a dosing interval as dictated above that maintains a central subfield thickness less than or equal to 300 microns or a complete absence of intraretinal or subretinal fluid on the macular cube. Once criterion A is met the dosing interval is again extended as outlined. If during a second extension period, criterion B is met, the patient is maintained at the dosing interval (less than where the second recurrence occurred) that maintains a central subfield thickness less than or equal to 300 microns or a complete absence of intraretinal or a subretinal fluid on the macular the second recurrence occurred) that maintains a central subfield thickness less than or equal to 300 microns or a complete absence of intraretinal or subretinal fluid on the macular cube for the rest of the study without further extension attempts.

All treatments will be administered at Cole Eye Institute at the Cleveland Clinic.

\*See Appendix B for detailed pre-injection procedures.

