#### 2.2 Secondary Objectives

The secondary objectives include:

- mean change from baseline in best-corrected visual acuity at months 6 and 12
- mean absolute change from baseline central foveal thickness at months 6 and 12 as measured by SDOCT (defined as the average thickness within the central 1 mm subfield)
- proportion of subjects that were anatomically "dry" by SDOCT at months 6 and 12
- proportion of participants who gained greater than or equal to 15 letters of vision at months 6 and 12
- proportion of participants who lost greater than or equal to 15 letters of vision at months 6 and 12
- proportion of patients that are 20/40 or better at months 6 and 12
- comparison of extent of angiography leakage from baseline to months 3, 6, and 12,
- comparison of peripheral nonperfusion from baseline to months 3, 6 and 12
- total number of injections

- Assessment of pre-trial anatomic improvement based on OCT on bevacizumab prior to switching to ranibizumab. Analysis will also be stratified based on subsequent response to ranibizumab.
- Assessment of pre-trial functional improvement based on snellen visual acuity prior to switching to ranibizumab. Analysis will also be stratified based on subsequent response to ranibizumab.

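### Criteria A and B give opposite instructions for a Group 2 eye with no fluid whose central subfield thickness rises above 300 microns, and two rules can place the Group 2 month-6 angiogram at different visits

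*Protocol*

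**What the plan says.** **Interval rules (Protocol 4.3.2b, Group 2, after the three loading doses).**

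- Criterion A applies "If the central subfield thickness is less than or equal to 300 microns or there is complete absence of intraretinal or" subretinal fluid. The interval then grows by 2 weeks, to at most 12.
- Criterion B applies "If on subsequent follow-up visits, the thickness increases above 300 microns or there is recurrence of fluid with thickness above 300 microns". The interval then falls by 2 weeks, to no less than 4.
- Criterion D adds: "If criterion B is met at any time, the patient will be reduced to a dosing interval as dictated above". It describes the state to be maintained as a thickness "less than or equal to 300 microns or a complete absence of intraretinal or subretinal fluid on the macular cube", and continues: "Once criterion A is met the dosing interval is again extended as outlined".

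**Month-6 angiogram, Group 2.**

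- Section 4.3.2b, within Criterion B, says: "Designated visits will also occur at 6 months and 12 months for visual acuity, ocular examination, FA, and OCT". No injection is given there unless a treat-and-extend visit falls at the same time.
- Section 4.5.1 (Group 2, months 3 to 11) and the Group 2 footnotes in Appendix A instead place the approximately six-month angiogram at the first visit after week 22. Both list an injection for those visits. The Group 2 flowchart has no column for a separate 6-month visit.

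**Context.** Group 1 has its angiogram at month 6 (4.5.1). On masking, 4.2 says: "The study is not masked". Section 2.2 lists "total number of injections" as a secondary objective, although 3.3.2 and 4.8.3 do not. Both 3.3.2 and 4.8.3 list leakage and peripheral nonperfusion at months 3, 6 and 12.

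**The concern.** Criterion A joins its two conditions with *or*, so absence of fluid is enough to extend at any thickness. The first limb of Criterion B needs only a rise above 300 microns, so it can shorten the interval in an eye with no fluid. Its second limb (fluid together with thickness above 300) is already contained in the first, so fluid cannot be read into B as a requirement. The same OCT result can therefore call for both a longer and a shorter interval.

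The interval is what separates the two arms after loading, and the study is open-label. If the text does not decide, the person who knows the arm and the patient's course must. That choice feeds directly into the injection count.

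The month-6 issue is one of timing. If some Group 2 eyes are imaged at a treat-and-extend visit soon after week 22 and others at a designated visit near month 6, the month-6 leakage and nonperfusion comparison with Group 1 mixes time points by scheduling accident.

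**Working it through.** The plan states no figure to reproduce here. The check is a truth table, followed by visit-day arithmetic.

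**1. Which criterion applies**

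| Thickness | Fluid | A (extend) | B (shorten) |
|---|---|---|---|
| ≤ 300 | absent | yes | no |
| ≤ 300 | present | yes | no |
| rises > 300 | present | no | yes |
| rises > 300 | absent | **yes** | **yes** |

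The last row is the only overlap.

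**2. Gap between the two next intervals**

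For a current interval of I weeks, gap = min(I + 2, 12) − max(I − 2, 4).

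| I | A gives | B gives | Gap (weeks) |
|---|---|---|---|
| 4 | 6 | 4 | 2 |
| 6 | 8 | 4 | 4 |
| 8 | 10 | 6 | 4 |
| 10 | 12 | 8 | 4 |
| 12 | 12 | 10 | 2 |

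**3. Injection count with one clash**

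Assumptions: nominal days; loading on days 0, 30 and 60; the loading interval treated as 4 weeks when the first 2 weeks are added, so the first extended interval is 42 days; extension at every visit other than the clash; injections counted before day 353 (month 12 as day 360, less 7). The text does not say whether the first extension is set at the month-2 or the month-3 visit, so both are shown.

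Extension set from the month-2 visit:
- A governs: 0, 30, 60, 102, 158, 228, 312 = 7.
- Clash at day 102, B governs: 0, 30, 60, 102, 130, 172, 228, 298 = 8.
- Clash at day 158, B governs: 0, 30, 60, 102, 158, 200, 256, 326 = 8.
- Clash at day 228, B governs: 0, 30, 60, 102, 158, 228, 284 = 7 (the next would be day 354).
- Clash at day 312, B governs: 7.

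Extension set from the month-3 visit:
- A governs: 0, 30, 60, 90, 132, 188, 258, 342 = 8.
- Clash at day 132, B governs: 0, 30, 60, 90, 132, 160, 202, 258, 328 = 9.
- Clash at day 188, B governs: 0, 30, 60, 90, 132, 188, 230, 286 = 8 (the next would be day 356).
- Clash at day 258 or 342, B governs: 8.

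A single clash therefore changes the count by 0 or 1.

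**4. Month-6 angiogram**

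Week 22 ends on day 22 × 7 = 154. Following every path of ±2-week steps within 4 to 12 weeks, the first treat-and-extend visit after day 154 falls on:
- day 158, 172 or 186, if extension is set from month 2;
- day 160, 174 or 188, if extension is set from month 3.

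With month 6 at day 180, the designated visit comes before days 186 and 188. It is then itself the first visit after week 22, and the two rules agree. On the other four days they pick different visits:
- 180 − 158 = 22 days
- 180 − 160 = 20 days
- 180 − 172 = 8 days
- 180 − 174 = 6 days

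Uninterrupted extension from month 2 gives day 158, the largest gap. Uninterrupted extension from month 3 gives day 188, with no conflict. Taking month 6 as day 183 instead changes the gaps to 25, 23, 11 and 9 days and leaves the pattern the same.

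**The case against.** **Criterion D may settle the first conflict.** It orders a reduction whenever B is met, which reads as giving B priority. This is the strongest reply, and it makes B the more natural reading. It does not close the matter. The state D aims for is again low thickness *or* no fluid, which this eye already satisfies. D resumes extension once A is met, and A is already met. D's own title concerns recurrence of fluid, which a dry eye does not have. No sentence says which criterion prevails.

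**The case is narrow and the effect small.** It needs a rise above 300 microns with no fluid at all, in a 30-patient pilot with a safety primary endpoint. That stands, and it limits the weight of the point.

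**The counts rest on conventions.** Section 4.3.2b permits an injection at month 12 if a treat-and-extend visit coincides, while 4.5.1 and Appendix A list none. Counting days 354 and 356 turns 7 versus 7 into 7 versus 8 (clash at day 228), and 8 versus 8 into 8 versus 9 (clash at day 188). The 0-or-1 range survives. Modelling one clash also leaves out Criterion D's bar on further extension after a second recurrence. As an illustration, clashes at days 102 and 172 with B governing give 0, 30, 60, 102, 130, 172, 200, 228, 256, 284, 312, 340 = 12, against 7 if A governs. The documents do not show how likely such a path is.

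**Visit windows blur the month-6 gap.** Section 4.3.2b gives no window for the 6-month visit, but ±7 days is used elsewhere. Day 174 would fall inside such a window and day 172 one day outside, so clear separation is left mainly to days 158 and 160. If windows run from the last treatment, Group 1's own month-6 visit could drift by up to 6 × 7 = 42 days. Appendix A also labels its visit as approximate. These points stand: the 6 to 22 days are nominal differences. They do not make the two rules one rule.

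**Conclusion.** Both inconsistencies are present in the current text.

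The criteria overlap in one of four thickness-by-fluid combinations. There they give next intervals 2 or 4 weeks apart, and a single occurrence changes the yearly injection count by 0 or 1 under the stated conventions. Repeated occurrences could change it by more. The number of eyes affected cannot be derived from the documents.

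The month-6 angiogram rules agree on some schedules and differ nominally by 6 to 22 days on others, taking month 6 as day 180 and no windows. This touches the month-6 leakage and nonperfusion comparisons. The angiogram rules do not conflict for month-6 acuity or OCT.

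The primary safety endpoint and the month-12 endpoints are unaffected. The point should be fixed because the remedy is simple, but it does not threaten the trial's main conclusion.

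**What to change.** 1. Reconcile Criteria A, B and D in 4.3.2b so that each combination of thickness and fluid status leads to exactly one action. A small table would do this. Which action applies is the sponsor's clinical decision.
2. Make 4.3.2b, 4.5.1 and Appendix A agree on one Group 2 month-6 assessment, with the same nominal time and window as in Group 1, and take all month-6 endpoints from it. State there whether an injection can be given at that visit.
3. State whether the first extension is set at the month-2 or the month-3 visit, since the injection schedule depends on it.

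The cost is protocol wording and one flowchart column. A designated 6-month visit is already described in 4.3.2b, so keeping it adds no visit to that section's schedule. If the sponsor prefers the week-22 rule, the change is equally one of wording, but the timing must then be aligned with Group 1.

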# c. Storage

Upon receipt, study drug kits should be refrigerated at 2°C - 8°C (36°F - 46°F). DO NOT FREEZE. Do not use beyond the expiration date. Ranibizumab vials should remain refrigerated. Protect vials from direct light. Store in original carton until time of use.

**RANIBIZUMAB VIALS ARE FOR SINGLE USE ONLY**. Vials used for one subject may not be used for any other subject.

# 4.4 CONCOMITANT AND EXCLUDED THERAPIES

During the study period, no additional intravitreal or periocular pharmacologics can be administered, including but not limited to bevacizumab, aflibercept, and steroids. Focal laser photocoagulation is also not permitted during the study period. Panretinal photocoagulation is allowed if an eye develops retinal neovascularization, optic disc neovascularization, anterior segment neovascularization, and/or vitreous hemorrhage thought to be related to neovascularization.

Subjects may continue to receive all medications and standard treatments administered for their conditions at the discretion of their treating physician.

#### 4.5 STUDY ASSESSMENTS

# 4.5.1 Assessments during the Treatment Period

# Screening/Day (-10 Days to Day 0)

After the patient/subject has provided informed consent, the following information will be collected:

- Inclusion/exclusion
- Informed consent documentation
- Demographics
- Medical history and concurrent illnesses
- Concomitant medications

- ETDRS visual acuity with manifest refraction
- Slit lamp examination

- Fundus examination
- Spectral Domain OCT evaluation
- Ultra-widefield fluorescein angiogram
- Pulse and blood pressure
- Weight

# **Treatment Period**

# Baseline/Day 0/Month 0 (may occur at same time as screening visit)

The following information will be collected:

- Inclusion/exclusion
- Informed consent documentation
- Demographics
- Medical history and concurrent illnesses
- Concomitant medications
- AEs

The following procedures and assessments will be conducted:

- ETDRS visual acuity with manifest refraction
- Slit lamp examination
- Fundus examination
- Spectral Domain OCT evaluation
- Intravitreal injection of ranibizumab
- Pulse and blood pressure

# Group 1 (Monthly treatment group): Month 1-Month 11 (+/- 7 Days)

The following information will be collected:

- Concomitant medications
- AEs

- ETDRS visual acuity with manifest refraction
- Slit lamp examination
- Fundus examination
- Spectral Domain OCT evaluation

- Intravitreal injection of ranibizumab
- Ultra-widefield fluorescein angiogram (months 3 and 6)
- Pulse and blood pressure

# Group 1 (Monthly treatment group): End of Treatment/Month 12 (+/- 7 Days)/Early Termination visit

The following information will be collected:

- Concomitant medications
- AEs

The following procedures and assessments will be conducted:

- ETDRS visual acuity with manifest refraction
- Slit lamp examination
- Fundus examination
- Spectral Domain OCT evaluation
- Ultra-widefield fluorescein angiogram
- Pulse and blood pressure
- Weight

# Group 2 (Treat-and-extend group): Month 1-Month 2 (+/- 7 Days)

The following information will be collected:

- Concomitant medications
- AEs

- ETDRS visual acuity with manifest refraction
- Slit lamp examination
- Fundus examination
- Spectral Domain OCT evaluation
- Intravitreal injection of ranibizumab
- Pulse and blood pressure

# Group 2 (Treat-and-extend group): Month 3-Month 11 Follow-up Interval Based on OCT criteria as outlined sections 3.1 and 4.3.2b

The following information will be collected:

- Concomitant medications
- AEs

The following procedures and assessments will be conducted:

- ETDRS visual acuity with manifest refraction
- Slit lamp examination
- Fundus examination
- Spectral Domain OCT evaluation
- Intravitreal injection of ranibizumab
- Ultra-widefield fluorescein angiogram [month 3 and 1st visit after week 22 of study entry (~ 6 month visit)]
- Pulse and blood pressure

# Group 2 (Treat-and-extend treatment group): End of Treatment/Month 12 (+/- 7 Days)/Early Termination visit

The following information will be collected:

- Concomitant medications
- AEs

- ETDRS visual acuity with manifest refraction
- Slit lamp examination
- Fundus examination
- Spectral Domain OCT evaluation
- Ultra-widefield fluorescein angiogram
- Pulse and blood pressure
- Weight

# Unscheduled visit

The following information will be collected:

- Concomitant medications
- AEs

The following procedures and assessments will be conducted:

- ETDRS visual acuity with manifest refraction
- Slit lamp examination
- Fundus examination
- Spectral Domain OCT evaluation
- Intravitreal injection of ranibizumab (optional based on investigators discretion if greater than 4 weeks since last injection)
- Pulse and blood pressure

# 4.5.2 Early Termination Assessments

Subjects who withdraw from the study prior to completion should return for an early termination evaluation **30** days ( $\pm$ **7** days) following the last injection/study visit for monitoring of all adverse events (serious and nonserious). The schedule of assessments for early termination is the same as that for the final visit.

#### 4.6 SUBJECT DISCONTINUATION

Subjects have a right to withdraw from the study at any time.

The subject may be withdrawn from the study for any reasons: if it is in the best interest of the subject, intercurrent illness, adverse events, or worsening condition. The Cole Eye Institute/Cleveland Clinic or [name] (Principal Investigator) may request the withdrawal of a subject because of protocol violations, administrative reasons, or any other valid and ethical reasons.

If a subject discontinues from the study, he or she will not be allowed to re-enter the study.

Reasons for subject discontinuation may include, but are not limited to, the following:

- Sensory rhegmatogenous retinal detachment or Stage 3 or 4 macular hole
- Investigator determination that it is not in the best interest of the subject to continue participation
- Pregnancy
- Need for anti-VEGF therapy other than ranibizumab in the study eye, unless as a part of the prospective investigational study design
- SAE
- Any other safety concerns

In the event of an adverse event in the study eye that is considered by the investigator to be severe in intensity, serious consideration should be given to discontinuing the subject from the study.

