# 1.4 NONCLINICAL EXPERIENCE WITH RANIBIZUMAB

#### 1.4.1 Nonclinical Pharmacokinetics

The pharmacokinetics of ranibizumab have been investigated in rabbits and cynomolgus monkeys following intravitreal and intravenous administration. In both species, following intravitreal administration, ranibizumab was cleared from the vitreous humor with a half-life of 2–3 days. Following single intravitreal administration to cynomolgus monkeys, retinal concentrations of ranibizumab were approximately one-third of vitreous concentrations and declined in parallel with vitreous concentrations. In humans, the intravitreal half-life of ranibizumab is estimated to be 9 days. Repeated intravitreal injections of ranibizumab can lead to detectable antibodies in serum in rabbits and cynomolgus monkeys.

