# Adverse Event Reporting Period

The study period during which all AEs and SAEs must be reported begins after informed consent is obtained and initiation of study treatment and ends 30 days following the last administration of study treatment or study discontinuation/termination, whichever is earlier.

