# f. Post-Study Adverse Events

If the investigator should become aware of an SAE occurring after a subject has completed or discontinued study participating if attributed to ranibizumab exposure, including, the development of cancer or a congenital anomaly in a subsequently conceived offspring of a female subject who participated in the study, this should be reported as an SAE.

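### A patient who needs a barred study-eye therapy has no compliant way to receive it and stay in follow-up, so Month 6 and Month 12 outcomes after exit are not collected

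*Protocol*

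**What the plan says.** Protocol Section 4.6 describes one kind of stopping, which is leaving the study. Its listed reasons include "Need for anti-VEGF therapy other than ranibizumab in the study eye, unless as a part of the prospective investigational study design". Adverse events, SAEs and a worsening condition are also grounds. The wording is permissive throughout, and re-entry is ruled out.

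Section 4.4 is not permissive: "During the study period, no additional intravitreal or periocular pharmacologics can be administered, including but not limited to bevacizumab, aflibercept, and steroids". It also bars focal laser, but allows panretinal photocoagulation for new neovascularisation or vitreous haemorrhage thought to come from it.

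For patients who withdraw, Section 4.5.2 plans one visit about 30 days after the last injection or study visit, and adds: "The schedule of assessments for early termination is the same as that for the final visit". Under Section 5.3, the adverse event reporting period "ends 30 days following the last administration of study treatment or study discontinuation/termination, whichever is earlier". Section 5.6.2 f keeps a later route open for some events: "If the investigator should become aware of an SAE occurring after a subject has completed or discontinued study participating if attributed to ranibizumab exposure".

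Section 4.8.3 places the acuity and OCT endpoints, including the responder proportions, at Months 6 and 12. Section 4.8.4 analyses available data without imputation. The SAP says that last observation carried forward can be used for early exits.

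**The concern.** Needing another drug or focal laser in the study eye is likely to reflect how that eye is doing on ranibizumab. If such a need ends follow-up, whether Month 6 and Month 12 outcomes are observed can depend on the outcome itself. The means and proportions at those visits may then describe a selected group. Neither analysis rule repairs this. An available-case analysis leaves the patient out, and carrying forward substitutes a value from before exit. Neither shows what happened afterwards. With 15 patients per arm, one or two such exits are visible in every proportion.

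**Working it through.** The documents give no discontinuation rate, and Section 4.8.1 says there was no formal sample size calculation. There is therefore no plan figure to reproduce. The check is what the text allows, then what is lost on exit.

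**1. Is exit forced, and is off-drug follow-up provided for?**

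| Situation | Must the patient leave? | Rule for follow-up after injections stop |
|---|---|---|
| Needs another anti-VEGF drug | Cannot receive it and comply with 4.4; 4.6 lists the need as a reason to leave | None |
| Needs intravitreal or periocular steroid, or focal laser | Cannot receive it and comply with 4.4; 4.6 makes protocol violations a ground for withdrawal | None |
| SAE or worsening | No; 4.6 leaves it to judgement | None |
| New neovascularisation treated with panretinal laser | No; 4.4 allows it | Not needed; injections can continue |

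Sections 4.3 to 4.7, the flowcharts in Appendix A and the SAP contain no rule for stopping ranibizumab and continuing to Months 6 and 12.

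**2. Efficacy visits lost (Group 1 schedule, Section 4.5.1).** Let m be the month of the last injection. The early-termination visit falls at about Month m + 1.

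- m = 3: visit at about Month 4; Months 6 and 12 are both lost.
- m = 5: visit at about Month 6, so only Month 12 is lost in practice.
- m = 6 or 9: Month 6 is already collected; Month 12 is lost.

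Group 2 intervals vary after the third dose, so there is no single schedule to work through for that arm.

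**3. Adverse event time not covered.** Collection ends no later than about Month m + 1, so the uncovered time to Month 12 is 12 − (m + 1) = 11 − m months:

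- m = 3: 8 months
- m = 6: 5 months
- m = 9: 2 months
- m = 11 (a completer's last injection): 0, as it should be

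**4. Is that time on drug?** Section 1.4.1 states: "In humans, the intravitreal half-life of ranibizumab is estimated to be 9 days". Thirty days is 30/9 = 3.33 half-lives, and 2^(−3.33) = 0.099. About 10% of a dose remains at day 30, so the uncovered time is mainly off treatment.

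**5. Bound on a Month 12 proportion.** If k of 15 patients in an arm have no Month 12 value, the full-arm proportion ranges from all k counted as failures to all k counted as successes, a width of k/15. The values of k are assumptions.

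| k | k/15 |
|---|---|
| 1 | 6.7 percentage points |
| 2 | 13.3 |
| 3 | 20.0 |

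**The case against.** The strongest reply is that the protocol seldom forces anyone out. Section 4.6 is permissive, so a patient with an SAE or worsening may stay. Assessment without an injection already exists: the Month 12 visits have none, the injection at an unscheduled visit is at the investigator's discretion, and for Group 2's designated Month 6 and Month 12 visits Section 4.3.2 b says "No treatment will occur at these visits unless the time coincides". Criterion C keeps worsening Group 2 patients in the study on 4-week dosing, and Group 1 is already on monthly dosing. This stands, and it limits the firm part of the point to patients who need a barred therapy. For the others, what remains is the absence of any rule to keep them in follow-up once injections stop.

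A second reply is that the stated interest is in ranibizumab after earlier anti-VEGF treatment, so a value taken after a switch partly measures something else. That is fair for the baseline-to-end comparison. For the comparison of randomised regimens, later values are still informative. The documents do not commit to either target, which is why the fix asks for both summaries.

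Third, the k/15 bound applies to any missing value, including withdrawal of consent or loss to follow-up, which this change would not recover. That also stands. The bound shows how sensitive an arm of 15 is, not how much this rule will cost.

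A reader might go further and infer that the primary safety endpoint is undermined. The documents do not support that. Section 2.1 concerns adverse events of ranibizumab. The triggering event is recorded, the early-termination visit collects all adverse events, and SAEs attributed to ranibizumab remain reportable if the investigator learns of them.

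**Conclusion.** The gap is real and cheap to close, and its weight is low. The combination of Sections 4.4 and 4.6 leaves a patient who needs a barred study-eye therapy no compliant way to have it and stay. Each such exit before Month 12 removes that patient's Month 12 outcomes, and an early one removes Month 6 as well. The 6.7 to 20.0 point range rests wholly on an assumed one to three missing patients in an arm.

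Two further inferences are tempting and not supported. One is that efficacy will look too favourable. The direction is not derivable, because a patient who left might have gone on to improve or worsen on the other therapy. The other is that power is damaged. The trial makes no power claim, so there is nothing to measure a loss against. The difference between Section 4.8.4 and the SAP on missing values is a separate matter and adds no weight here.

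**What to change.** - **Section 4.6:** separate stopping study injections from withdrawing consent, leaving the decision to stop injections as it is. Unless consent is withdrawn, keep the existing Month 6 and Month 12 acuity, OCT, eye examination and adverse event collection.
- **Section 4.4:** state that any otherwise barred study-eye therapy (other anti-VEGF drug, steroid or focal laser) given after ranibizumab is stopped is recorded and does not force exit.
- **Section 5.3:** for these patients, collect adverse events through Month 12. Report those occurring more than 30 days after the last dose, or after a switch, separately from on-treatment events.
- **Analysis:** summarise by randomised arm with post-switch data flagged, and add a summary restricted to data before any switch.

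The cost is one amendment to three protocol sections, with matching analysis text. No new visit type is needed, since the Month 6 and Month 12 visits are already scheduled. A few patients would make one or two visits after stopping injections. Post-switch values would partly reflect another therapy, and the split summaries may rest on very few patients.
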